## 5.4 Secondary outcomes

The following secondary endpoint will be measured:

- number of patients not dispatched to as travel time too great/team unavailable
- number of patients in whom it is attempted to start inserting guidewires but do not meet study inclusion criteria at 20 minute time out.
- the number of patients successfully cannulated between 31 and 45 minutes
- the number of patients successfully cannulated between 46 and 60 minutes
- proportion of patients who achieve ROSC prior to the 20 minutes timeout
- the number of patients in refractory cardiac arrest at 20 minutes in whom ROSC is achieved prior to ECMO flow
- time interval between call to the emergency services and ECPR team arrival
- proportion of potentially supportable patients in whom guidewire placement is attempted
- organ dysfunction during the first five days of hospital stay
- survival to hospital discharge
- neurological outcome at hospital discharge (Cerebral Performance Category and modified Rankin scales)
- incidence of ECPR-related complications (failure to cannulate, vascular injury, site infection and distal leg ischaemia)

Details about resources used and health economic data will be collected to estimate the range of costs and affordability of any subsequent clinical trial or clinical service. These data will include:

- ECMO equipment used
- duration of ECMO support
- duration of intensive care unit stay
- maximum organ support on the Intensive Care Unit (ICU)
- duration of acute hospital stay
- duration of inpatient rehabilitation following acute hospital stay

## 6. Study population

### 6.1 Inclusion criteria

Male or female patients with a known or visible age of 18 to 65 years who:

- have a witnessed out-of-hospital cardiac arrest
- a presumed cardiac aetiology to their cardiac arrest
- receive bystander chest compressions within 3 minutes
- remain in cardiac arrest at 20 minutes following collapse or fail to sustain ROSC in the pre-hospital setting

Out-of-hospital cardiac arrest encompasses both those who arrest prior to the emergency services being called and those who are witnessed to arrest by the emergency services. For the purpose of this study patients who suffer their first cardiac arrest whilst in transit to hospital will not be included.

## 6.2 Exclusion criteria

The following patients will not be suitable for entry into the study:

- Known to be are visibly appear younger than 18 years old or older than 65 years.
- Known or visible advanced pregnancy (when resuscitative hysterotomy should be performed)
- No signs of life (physical movement or breathing) AND evidence of ineffective chest compressions suggested by:
  - absence of electrical activity at 20 minutes time out OR
  - end tidal carbon dioxide level of less than 1.3 kPa (10 mmHg)
- Evidence from others present at the scene or patient examination that ECMO unlikely to benefit patient (e.g. advanced malignancy, severe frailty). The narrative of this decision will be recorded in the Case Record Form (CRF).

# 7. Study design

## 7.1 Overall design

The study is a feasibility study of a complex intervention performed on two study sites.

## 7.2 Setting and timescale

The study will be undertaken in North East London over approximately 12 months. The study site is Barts Health NHS Trust.

## 7.3 Timescale

The study will only be performed on study days when the ECMO team is available. It is anticipated that this will be 2-3 days per week. It is anticipated that it will take up to 52 study days to recruit six patients.

## 7.4 Patient identification / ECPR Team activation

On study days, the ECPR team will be active in a fast response blue light emergency response car provided by London's Air Ambulance. They will have no other clinical or non-clinical duties. On study days, the team will assemble at the Royal London Hospital and perform challenge/response checks on their equipment and vehicle. Once complete they will inform control that they are active and available. At various points in the day the team will be based in geographical areas where London Ambulance Service have attended the most cardiac arrests historically. At the end of the shift the team will inform control that they are standing down.

The team will be activated by the Advanced Paramedic Practitioner (APP) desk in the Emergency Operations Centre at London Ambulance Service. This desk screens in real time all calls to the emergency services that may be a cardiac arrest and dispatch additional APPs to the scene. They listen in on all calls where it is indicated on the pre-triage questions, asked by the call handler, that the patient is not breathing or has abnormal breathing. In addition, they screen calls as requested by the dispatchers. Their clinical experience at listening to calls will enable the LAS sit to identify trial subjects and dispatch the ECPR team as an additional emergency response within 2-3 minutes of the emergency call being placed. They will task the ECPR team if the estimated time of travel to the scene is 20 minutes or less.

All 'patients' for whom the team is activated will be included in the screening log. In addition to patients who are enrolled and receive ECMO, the log will indicate those people who were never assessed (as the team was stood down prior to arrival), those whose were assessed but clearly

did not meet inclusion/exclusion criteria (Section 8.2) and those in whom guidewires were inserted but were not formally enrolled in the study at the 20 minute time out (Section 8.5)

### **7.5 Consent waiver at enrolment**

Patients are unable to provide consent to enter the study at the point of enrolment as they lack capacity since they are unconscious and in cardiac arrest. This situation is sudden and unexpected preventing prior consultation with the patient and prospective consent. Their capacity will not vary throughout the intervention period as they will remain in cardiac arrest and unconscious. Since there are no alternative groups of patients in whom this study could be conducted it is necessary to recruit patients who lack capacity.

It is unlikely that if it were possible to consult a personal consultee, in the context of the distress of learning the patient is in cardiac arrest, that any such person could be able to make an informed decision in the limited time available.

Since delays in resuscitation and emergency treatments are associated with worse patient outcomes, it is not practical in this study to consult a professional consultee, such as their general practitioner, without placing the participant at potential harm from delayed treatment.

Therefore, patients will be enrolled without specific consent at the start of the study if they meet eligibility criteria. This was specifically discussed at a patient and public engagement event (Section 12) and was considered universally acceptable by the attendees.

If a patient is wearing a MedicAlert bracelet that indicates they have indicated an Advance Decision about their care, and there is sufficient time to find out about the Advance Decision then this will be undertaken and respected if the Decision is considered to be valid and within the context of the clinical scenario. An indication by a patient that they would not wish to receive blood products will not preclude them receiving ECPR. Any Advance Decisions will be discussed with the Barts Health NHS Trust legal team at the earliest opportunity.

### **7.6 Consent to on-going inclusion in the study**

ECMO support will be life-sustaining. A personal consultee will not be asked if the participant should remain in the study. Nevertheless, they will be consulted about the patient's other medical conditions and likely wishes and these will be considered, according to standard clinical practice, by the attending physicians who will not be study investigators. Family and friends of study participants will be given information about the study as soon as is practicable.

Participants will be approached if they regain capacity to inform them of their participation in the study. This will be done prior to hospital discharge and usually on the hospital ward when they are no longer critically unwell. Individual patients can ask to be withdrawn from the study if they request to do so. Data already collected will be processed. The legal basis for processing these data, which include special category data, is as a task in the public interest as outlined in General Data Protection Regulation and the Data Protection Act (2018). Patients will not be required to provide a reason for wanting to withdraw from the study. Withdrawal will not influence the goals of on-going medical care for a patient.

### **7.7 Provision of public information about the study**

We will disseminate information about the study through LAS, Barts Health, and London Air Ambulance. Media used for information will include the internet, newsletters, posters, annual reports and discussion at public meetings. The public will be directed to the trial website for further information.

People will be able to decline participation in the trial in the event they sustain a cardiac arrest. Requests not to participate will be sent to the Chief Investigator who will ensure that a stainless steel "No Sub30 study" bracelet is issued to the person's home address.

## **7.8 Co-enrolment in other clinical studies**

[figure not shown]
Patients in Sub30 are eligible for co-enrolment in other studies and the scientific validity of this will be decided by the Chief Investigator on a case by case basis in keeping with the UK guidelines for critical care research [21]. Co-enrolment with any studies should be documented in the CRF.

## **7.9 End of study**

The end of the study is defined as 90 days after the final patient is recruited into the study.

The study will be discontinued early if the sponsor or Data Safety and Monitoring Committee request the study to be stopped. The Trial Steering Committee will advise how to manage patients receiving ECMO as study participants when this decision is made.

## 7.10 Study Scheme Diagram

## 8. Study procedures

The delivery of pre-hospital ECMO is a complex procedure that encompasses dispatch of the eCPR team to the patient, assessment, institution of ECMO, transfer to Heart Attack Centre and then on-going care at the Heart Attack Centre in the cardiac catheterisation laboratory, intensive care unit and ward. Full details are provided in the latest approved version of the Study Manual. This section contains a synopsis of the key aspects of care.

## **8.1 ECPR Team members**

The ECPR team will comprise of:

- A pre-hospital emergency medicine consultant
- An advanced paramedic practitioner/Helicopter emergency medical paramedic
- Two ECMO consultant as defined in the St Bartholomew's Hospital Local Policy for Accreditation of medical and nursing staff as ECMO specialists (SBH-POL-01-2016-012 or any superseding version)

Only the ECMO consultants will perform the ECMO intervention on the study subjects (Sections 8.6 and 8.7), and the other members of the ECPR team as detailed in Section 8.3 are available for medical support, but will act as observers in relation to ECMO management.

## **8.2 Primary assessment**

All team members will follow the current Barts Health NHS Trust and London Ambulance Service NHS Trust procedures regarding protection of patients and staff from SARS-CoV-2 infection. On arrival at the scene the ECPR team will assess whether the inclusion criteria or exclusion criteria are met. They will also undertake a comprehensive bilateral assessment of the pupillary response to light using an automated pupillometer (NPI-200, NeurOptics, Irvine, California).

If the inclusion and exclusion criteria are definitely not met they will:

- Assist alternative LAS resources present on scene as required. Once assistance is no longer required the ECPR team will stand down and inform control that they are available for further tasking to cardiac arrests.
- Provide the primary response, if there are no LAS resources on site, irrespective if the patient is in cardiac arrest or not. They will use standard LAS treatment protocols. Upon arrival of alternative LAS resource then the ECPR team will hand over care of the patient to that resource and stand down unless on-going assistance is required by LAS. On standing down the ECPR team will indicate to control that they are available for further tasking to cardiac arrests.

If inclusion criteria are met and no immediate exclusion criteria identified, then ECPR pre-hospital team members (Pre-hospital medicine consultant and paramedic) will split from the two ECMO consultants who will concurrently fulfil their roles and responsibilities.

## **8.3 ECPR Pre-hospital team roles and responsibilities**

The pre-hospital ECPR team will endeavour to achieve ROSC by delivering and supporting others in delivery of ALS to the patient. They will:

- introduce the ECPR team to any on scene healthcare resources
- manage the cardiac arrest following London Ambulance Service and Resuscitation Council ALS Guidelines
- seek ROSC by addressing reversible causes, ensuring advanced airway management and optimising resuscitation including automated mechanical compressions
- administer intravenous fluids to aid percutaneous cannulation by the ECMO team as required
- manage the pre-hospital environment and ensure team safety
- establish 360 degrees access to the patient
- establish collateral history about the patient, the collapse, and the timings of resuscitation attempts
- prepare for team timeout if cardiac arrest is refractory at 20 minutes of resuscitation by healthcare professionals

## **8.4 ECMO consultants' initial roles and responsibilities**

The ECMO consultants will establish a sterile surgical area in the patient's groin and using real-time ultrasound guidance to percutaneously insert guide wires into the patient's femoral artery and vein. The position of wires in the aorta and inferior vena cava respectively will be confirmed using

subcostal/trans-hepatic ultrasound. They will also complete the priming of the CardioHelp circuit so it is ready for use. If chest compressions must be interrupted for insertion of the needle/guidewire then this will be for no more than ten seconds (as timed by the consultant in pre-hospital medicine) and attempts made to coordinate these with any pulse checks.

If ROSC is achieved prior to 20 minutes of resuscitation then any wires present at that point will be used to insert 6Fr angiography sheaths into the femoral artery and/or vein to facilitate care at the Heart Attack Centre. The team will then continue to support LAS as required to provide standard post-resuscitation care and expedited transfer to the nearest Heart Attack Centre.

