### **8.5 Twenty minute time-out if patients remains in cardiac arrest**

Twenty minutes after the start of resuscitation by a healthcare provider a team time out will be called. Cardiopulmonary resuscitation will continue during this time out.

The pre-hospital consultant will present the patient using the Situation Background Assessment Recommendation (SBAR) format. The assessment will include reciting the inclusion and exclusion criteria in a challenge response manner. If the team considers that there are no exclusion criteria met then the ECMO consultants will proceed to cannulate the patient's femoral artery and vein and commence ECMO support. In the interval between 20 minutes of resuscitation and ECMO support, no more epinephrine (adrenaline) boluses will be administered. If chest compressions must be interrupted for insertion of the cannulae then this will be for no more than ten seconds (as timed by the consultant in pre-hospital medicine).

If an exclusion criterion is identified then any wires present at that point will be used to insert 6 Fr angiography sheaths into the femoral artery and/or vein which may facilitate on-going care. The team will then continue to support LAS as required. All patients will be followed up for adverse events related to the insertion of guidewires for seven days following the cardiac arrest. No other data, other than that included in the screening log, will be collected for these patients.

If cannulation cannot be achieved within 60 minutes then further attempts will not be continued and the patient reviewed and consideration made to declare life extinct or transport the patient under ongoing CPR to the nearest emergency department.

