## 16. Safety reporting

### 16.1 Adverse Events (AEs)

An AE is any untoward medical occurrence in a participant to whom an intervention has been administered, including occurrences which are not necessarily caused by or related to that intervention. An AE can therefore be any unfavourable or unintended sign (including an abnormal laboratory finding), symptom or disease temporally associated with study activities.

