4.1.4 Subgroup definitions

Not applicable.

5 Patient Disposition

Participants will be patients with a visible age between 18 and 65 who have a witnessed out-of-hospital cardiac arrest with presumed cardiac aetiology, receive bystander chest compressions within 3 minutes and remain in cardiac arrest or fail to sustain ROSC at 20 minutes. Exclusion criteria are detailed in the protocol section 6.2. Numbers enrolled, withdrawing and completing discharge and 3 month follow-up will be reported.

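### Femoral guidewires are placed before formal enrolment, and the protocol does not say how wired patients with early ROSC are to be informed or followed up for harm

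*Protocol*

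**What the plan says.** Protocol 8.2 and 8.4 have the ECMO consultants start on the femoral vessels once the first assessment finds no reason to stop, while conventional resuscitation continues. For early return of circulation, 8.4 states: "If ROSC is achieved prior to 20 minutes of resuscitation then any wires present at that point will be used to insert 6Fr angiography sheaths". The patient then goes to the nearest Heart Attack Centre.

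Formal entry comes later. The screening log in 7.4 includes "those in whom guidewires were inserted but were not formally enrolled in the study at the 20 minute time out". SAP section 5 describes participants as people who, among other criteria, "remain in cardiac arrest or fail to sustain ROSC at 20 minutes". Protocol 7.5 puts the moment more loosely: "patients will be enrolled without specific consent at the start of the study if they meet eligibility criteria".

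The rules on information and safety use the word participant. Section 7.6, repeated in 11.4, says: "Participants will be approached if they regain capacity to inform them of their participation in the study". Section 16.1 says: "An AE is any untoward medical occurrence in a participant to whom an intervention has been administered".

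Section 8.5 adds, after describing patients found to be excluded at the time-out: "All patients will be followed up for adverse events related to the insertion of guidewires for seven days following the cardiac arrest". Its next sentence limits all other data on these patients to the screening log.

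**The concern.** Guidewire placement is a study procedure, and it is invasive. It happens before the point at which the protocol formally counts someone as enrolled. Anyone wired whose circulation returns and holds before 20 minutes has therefore been exposed to the study without being enrolled in it.

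Two things are at stake. The first is ethical. A survivor who had a femoral artery and vein instrumented by a study team, without consent, has no written entitlement to be told.

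The second is statistical. Protocol 4.5 defends early wiring partly on its low risk of complications, and this study is the chance to observe that risk. Section 11.4 describes the first 20 minutes as the period when ROSC is most likely, so a larger trial would expose such patients too. If their harms are not looked for, silence may be read as absence of harm.

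**Working it through.** The plan gives no figure on this point, and no power calculation was done, so the main check compares what the documents provide for three groups of wired patients.

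| Provision | Proceeds to cannulation at the time-out | Excluded at the time-out (8.5) | Sustained ROSC before 20 minutes (8.4) |
|---|---|---|---|
| Formally enrolled (7.4) | Yes | No | No |
| 6 Fr sheath over the wire | Not described | At or after the time-out | Before the time-out |
| Destination | St Bartholomew's once on ECMO (8.7) | Not fixed; team supports LAS | Nearest Heart Attack Centre |
| Told of the study (7.6, 11.4) | Yes, as a participant | No text | No text |
| Within the AE definition (16.1) | Yes | Only if a participant | Only if a participant |
| Seven-day guidewire follow-up | Full study data collection | Yes, stated | Not stated in 8.4 |
| SAE reporting (16.3, 16.5) | Yes | No enrolment condition stated | No enrolment condition stated |

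**Reach of the seven-day sentence.** Its subject is all patients, which could be read broadly. But the next sentence says nothing beyond the screening log will be collected on these patients. That cannot be true of enrolled patients, so the sentence does not cover everyone. It certainly covers those excluded at the time-out, whom its paragraph describes. Whether it also covers the 8.4 group cannot be settled from the text: 8.4 has no follow-up sentence and no reference to 8.5.

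**How a harm would reach the study.** The synopsis names Barts Health and LAS as the research sites. In 16.5 the 24-hour clock starts when the site is notified. Neither document says how a receiving hospital that is not a site would notify anyone. The follow-up is also worded for guidewire insertion and does not name the sheath that may be left in place.

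**Counts.** The secondary outcomes in 5.4 count patients with ROSC before the time-out and patients in whom wiring was attempted but who did not qualify. They do not count harms in either group.

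**Illustration under assumptions.** Let *q* be the share of wired patients with sustained ROSC before 20 minutes, and suppose all the others are cannulated. Per six cannulated patients, the expected number in the 8.4 group is 6*q*/(1 − *q*):

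- *q* = 10%: 0.6/0.9 = 0.7
- *q* = 30%: 1.8/0.7 = 2.6
- *q* = 50%: 3.0/0.5 = 6.0

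Take the last case, six such patients, with an assumed wire or sheath harm rate *h*. The chance of at least one event is 1 − (1 − *h*)^6:

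- *h* = 2%: 11%
- *h* = 5%: 26%
- *h* = 10%: 47%

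If none of six fully followed patients had an event, the one-sided 95% upper limit would be 1 − 0.05^(1/6) = 39%. Complete follow-up would not give a precise rate. It would show how many patients were actually checked.

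**The case against.** Much can be said for the protocol as it stands.

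- **Follow-up exists.** A reader might infer that guidewire harm will be under-recorded in every wired patient who is not enrolled. The documents do not support that: 8.5 promises active seven-day follow-up, and it expressly reaches those excluded at the time-out. The doubt is confined to the 8.4 group.
- **The SAE route is not closed.** A reader might infer from 16.1 that these patients fall outside it. But the SAE definition in 16.3 is not tied to participants, and 16.5 covers all SAEs and relatedness to any research intervention. This is an ambiguity, not an exclusion.
- **Sheaths do not always precede the time-out.** They do so only with early ROSC; in patients excluded at the time-out they come at or after it.
- **7.4 and 7.5 can be reconciled.** Eligibility in 6.1 requires continuing arrest at 20 minutes or failure to sustain ROSC, so both can mean entry at the time-out. This stands, but it confirms that patients with sustained early ROSC are never enrolled.
- **The Study Manual may help.** Sections 8 and 15.2 place the detail of care and transfer after ROSC there, and it was not available for this review. It may say how receiving hospitals are contacted. Participant status and the duty to inform are nevertheless set in the protocol, and they are what need settling.

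**Conclusion.** The point holds in a limited form. No text provides for informing a wired survivor who is never enrolled; this rests on wording alone and on no rate. It is unclear whether the seven-day follow-up and SAE reporting reach patients with ROSC before 20 minutes, so wire and sheath harms in that group may be missed. The documents do not show that they will be, nor that any complication rate would be biased towards zero.

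The size is unknown. It is tempting to use the protocol's background rates: 35.5% without ROSC in the Utstein comparator group gives 6 × 0.645/0.355 = 10.9 patients with ROSC per six without, and 70% without sustained ROSC over all cases gives 6 × 0.30/0.70 = 2.6. Neither figure supports an estimate. They describe ROSC at any time, including before the team arrives and after 20 minutes, and they leave out wired patients excluded at the time-out. The range of 0.7 to 6 shown above rests wholly on assumed values of *q*.

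SAP 4.1.3 restricts the safety population to cannulated patients, so events in other wired patients have no planned table. That concerns analysis and does not show a failure to record.

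**What to change.** 1. State in 7.4, 7.5 and section 16 that a person counts as a participant, for the information duty in 7.6 and for safety reporting, from the first guidewire attempt. Keep the time-out as entry to the ECMO stage, so the target of six is unaffected.
2. Apply the seven-day follow-up expressly to 8.4 patients, and word it for events related to wires or sheaths.
3. Record the receiving hospital and make an enquiry there at day 7.
4. Report events over the number of wired patients with completed follow-up, and show non-replies as unknown. Add this table to the SAP beside the safety analysis of cannulated patients.

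The cost is a protocol amendment, wording for patient information, a few more SAE forms and a small number of day-7 enquiries, some of which 8.5 already promises. No change to clinical management is proposed.
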